**MOTHER SUBJECTS:**

1. Patients aged 18 years or more, who are able to consent.

2. Singleton pregnancy.

3. Gestation at randomization prior to 31 weeks plus 5 days or so that occlusion is done at the latest on 31 weeks plus 6 days.

4. Estimated to have moderate pulmonary hypoplasia, defined prenatally as:

- O/E LHR 25-34.9% (included; irrespective of the position of the liver) • O/E LHR 35-44.9% (included) with intrathoracic liver herniation as determined by ultrasound or MRI.
- The O/E LHR will be determined by the FETO centers as follows:
  - Measurement of the contralateral lung area preferentially by the tracing method at the 4-chamber view of the heart; if by other method adjusted normative ranges must be used.
  - Measurement of the head circumference at the standard biparietal view of the head.
  - The observed lung area: calculation of the LHR as the ratio of the measurements of the lung area to head circumference.
  - The expected lung area is the lung area of a normal gestational age match, as determined by the head circumference of the index case in a normogram established for the same measurement method (tracing method in this case). A calculator for this will be available on the website of the study.
  - Calculation of the observed over expected lung area.

5. Acceptance of randomization and the consequences for the further management during pregnancy and thereafter, this includes the required observation following FETO surgery, which lasts approximately 4 weeks after balloon is in place, until balloon is removed.

6. The patients must undertake the responsibility for either remaining close to, or at the TCH FETO center, or being able to travel swiftly and within acceptable time interval (within 30 minutes) to the TCH FETO center until the balloon is removed. Intended postnatal treatment center must subscribe to suggested guidelines for “standardized postnatal treatment.”

7. Provide written consent to participate.

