#### **6.5 Balloon Removal**

Balloon retrieval will be planned at between 34+0/7 and 34+6/7 weeks; at the discretion of the FETO center.

In the event of a patient relocating after having the balloon placed, despite having committed to remain in the area during consent process, she will be asked to return for the removal. Every effort to make arrangements for her to be managed by the nearest center capable of an EXIT procedure

or balloon retrieval (San Francisco or Philadelphia) will be made.

The optimal method for balloon retrieval (fetoscopic versus ultrasound guided percutaneous) will be decided case by case by the FETO team based on fetal position and fetal lung response.

Betamethasone (12 mg IM, 2 doses given 24 hours apart) will be given to the mother preoperatively to improve fetal lung compliance prior to removal if indicated.

Anesthesia, sedation, and tocolysis for the balloon retrieval will be as described above for the balloon placement.

Endoscopic balloon removal:

- As with placement of the balloon, fetoscopic/endoscopic retrieval will use a 9-12 Fr Teflon cannula loaded with a pyramidal trocar that is inserted into the amniotic cavity.
- A Storz endoscope or Storz fetoscope will be passed through the cannula into the amniotic fluid and maneuvered into the fetal larynx as noted above.
- The balloon will be visualized, punctured, grasped, and removed.
- The fetoscope/endoscope and cannula will be then removed.

Ultrasound guided balloon removal:

- Using a 22G needle and continuous ultrasound guidance the balloon will be punctured.
- The deflated balloon will be flushed from the trachea by the egress of pulmonary secretions distal to the occlusion. Recovery post balloon removal:

- The mother will then recover in the usual way and be discharged once stable.
- After removal of the balloon, patients will have the choice of delivering at Texas Children's Hospital Pavilion for Women with the CDH managed and repaired at TCH, or returning to their obstetrician for delivery with subsequent repair of the CDH by the pediatric surgeons at their referring facility.
- Given the severity of the CDH, the baby will need to be delivered in a facility that has the capability of immediate pediatric surgery services.

Balloon retrieval reattempts:

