#### Secondary Analyses:

A secondary analysis will compare the proportion of subjects that survived until discharge from the hospital in the two treatment groups, and those free of oxygen need at 6 months of age with an as-treated (“per protocol”) analysis.

Data will also be analyzed depending on the case load at each postnatal treatment center, i.e. treatment centers with a case load above, respectively under 6/year.

Whenever possible, analysis of outcomes of non-randomized subjects will be made to provide the most complete synthesis of the data. We will keep data from any non-randomized patient that receives a FETO balloon on a compassionate basis and we will analyze the data in a separate analysis.

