- The number of centers recruiting for postnatal treatment cannot be anticipated at this time. This will by definition be uncontrollable, and it may influence the outcome in either group. This is an accepted source of error by the investigators because it is a clinical reality (this is an effectiveness or pragmatic trial). The organizers do not have funding, neither the power nor logistics for having all postnatal management at one location. Guidelines for standardization of postnatal treatment are therefore being issued (Appendix I), which will reduce the impact of this source of error. An important source of error may also be case load at each of these participating centers. For that reason a post hoc analysis will be made according to the case load during the study period.
- Subjects randomized to postnatal care who seek fetal intervention elsewhere, may reduce study power. The consortium of FETO centers will not perform FETO in patients eligible for the present study, outside the herein described RCT. This seems ethical as FETO-treatment for this particular severity group so far has not been offered by the FETO consortium, and to their knowledge neither elsewhere.
- The extent to which non-FETO centers will carry out FETO in patients that are eligible for the herein proposed RCT cannot be estimated. Maximum efforts will be done to reduce the number of such centers. One method is to include those centers based on the criteria outline below. During the course of this study, other prenatal treatment centers have expressed their interest to join this study. If they are not or less experienced, this may be a source of error. The steering committee has met on this issue and has defined empirically criteria for eligibility for study participation, following which they may apply locally for ethics committee approval and ultimately they may participate to the present study under the same conditions as herein.

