- Preterm pre-labor rupture of the membranes and as a consequence preterm labor prior to in utero reversal of the occlusion, with as a consequence "incomplete" prenatal therapy as well as problems directly due to the inability or difficulties to remove the balloon, may result in lower than expected survival chances. When this happens, it will cause delivery at one of the FETO centers, therefore leading to a higher than expected number of babies delivered at these institutions. However this is inherent to the prenatal therapy and not avoidable. A separate secondary analysis may be done as to judge on the biological effect of the complete course of prenatal therapy (balloon insertion and balloon removal followed by birth in the un-occluded state), but again, results will be reported on an intention to treat - basis.
- In the fetal treatment arm there is the potential of patients not complying during the period the airways are plugged, presenting in an emergency at their local center, or for whatever reason not returning to the FETO center for balloon removal. This may adversely affect the outcome in the treatment group, lead to a higher than expected death rate in that arm. It could only be

discounted by post hoc exclusion. This will however not be done, as it is considered as an inherent risk of prenatal therapy. Such an effect may however be documented in a secondary analysis as described above.

- Prenatal medical imaging techniques may fail to recognize a concomitant congenital anomaly that is therefore only diagnosed after birth. Since serious associated anomalies are an independent predictor of outcome, and their numbers should be low, patients may not be equally distributed in both treatment arms. These patients will be excluded post hoc from analysis. It will include patients with serious genetic anomalies (not known at the time of FETO), undiagnosed structural cardiac or other structural anomalies that directly compromise neonatal outcome. Analysis of cases to be excluded will be overseen by the Data Monitoring and Safety Committee (also referred to as Oversight Committee).

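### Grouping infants by the case load of the treating centre lets FETO alter the groups, so comparisons of the arms within load groups can be biased

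*Combined protocol and SAP*

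**What the plan says.** Section 9.2, Secondary Analyses, announces: "Data will also be analyzed depending on the case load at each postnatal treatment center", and splits centres by "case load above, respectively under 6/year". The list of error sources later in Section 9.2 returns to this: "a post hoc analysis will be made according to the case load during the study period". Neither place says whether the centre is the one planned at entry or the one that treated the infant. The eligibility criteria for mothers in Section 5.2 do name the planned one: "Intended postnatal treatment center must subscribe to suggested guidelines".

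The same list of error sources describes what happens in the FETO arm when the membranes rupture and labour begins before the occlusion is reversed: "it will cause delivery at one of the FETO centers, therefore leading to a higher than expected number of babies delivered at these institutions". It adds that such events "may result in lower than expected survival chances". Section 6.5 gives a second route by which the arm can affect the centre: "After removal of the balloon, patients will have the choice of delivering at" the Texas hospital, with repair there, or of going back to the referring side for both.

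**The concern.** A subgroup comparison of randomised arms is protected by randomisation only if the subgroup is fixed before treatment can act on it. Here the grouping variable is, on the natural reading, the treating centre. The protocol itself says that events arising only while a balloon is in place change where the infant is born and may worsen survival. If those infants are then treated where they were born, the FETO infants in a load group are no longer the counterparts of the control infants in that group.

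Counting load during the study adds a second difficulty, because diverted infants can raise the count at the receiving centre and lower it at the intended one.

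Section 9.2 calls case load an important source of error and offers this analysis as its response. A reader who sees different FETO effects in high-load and low-load centres may put them down to centre experience when part of the difference comes from how the groups were formed.

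**Working it through.** **The plan's own figure.** The plan gives no number for the case-load analysis. The nearest figure is the 98 per arm in Section 9.1. The unpooled formula for 40% v 60%, one-sided 2.5%, 80% power gives (1.960 + 0.842)² × (0.4×0.6 + 0.6×0.4) / 0.2² = 94.2. The O'Brien-Fleming plan with looks at 40, 60, 70, 80, 90 and 100% of information has a simulated inflation factor of 1.040, and 94.2 × 1.040 = 97.9. So 98 reproduces, and nothing below changes it.

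**Illustration for the case-load groups.** Suppose FETO has no effect on any infant, and some FETO-arm infants intended for low-load centres are treated at high-load ones.

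- h = share intended for high-load centres: 0.5 (assumption).
- p_L, p_H = survival by intended group: 35% and 45% (assumption; they average the 40% control rate of Section 9.1).
- s = share of low-load FETO cases that change group (assumption). The only related figures are membrane-rupture risks: 15% within 3 weeks (Section 2.0) and 11% to 35% (Section 7.2). These are proxies.
- p_D = survival of the diverted: 20% to 30% (assumption; the plan says only that survival may be lower).

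With grouping by treating centre, survival in the FETO arm becomes:

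- Low-load: (p_L − s·p_D) / (1 − s), against p_L in controls.
- High-load: (h·p_H + (1−h)·s·p_D) / (h + (1−h)·s), against p_H in controls.

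For s = 15% and p_D = 20%:

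- Low-load: (0.35 − 0.03) / 0.85 = 0.376, which is +2.6 points.
- High-load: (0.225 + 0.015) / 0.575 = 0.417, which is −3.3 points.
- Contrast between groups: 5.9 points, where the truth is zero.

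| s | p_D | Low-load difference | High-load difference | Spurious contrast |
|---|---|---|---|---|
| 5% | 30% | +0.3 | −0.7 | 1.0 |
| 7.5% | 20% | +1.2 | −1.7 | 3.0 |
| 11% | 30% | +0.6 | −1.5 | 2.1 |
| 15% | 20% | +2.6 | −3.3 | 5.9 |
| 35% | 20% | +8.1 | −6.5 | 14.6 |

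**Sensitivity to the baseline.** With 50% survival in both groups and h = 0.5, the contrast is 6.1 points for s = 15% and p_D = 30%. It runs from 2.0 (5%, 30%) to 23.9 (35%, 20%). Diverted infants need not be sicker than their own group for an artefact to arise. With p_H = 60%, p_L = 40%, p_D = 40% and s = 15%, the low-load difference is 0 but the high-load difference is −2.6.

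**Grouping by intended centre.** No infant changes group, so under the same assumptions both differences are 0.

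**Scale against noise.** With 98/2 = 49 per arm in a load group, the 95% half-width of one difference is 1.96 × √(0.48/49) = 19 points. For the contrast of two such differences it is 19.4 × √2 = 27 points.

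**The case against.** - **The text does not say actual centre.** Correct. That reading is an inference from the use of the word intended in Section 5.2 and its absence in Section 9.2. If the intended centre was meant, the plan needs to say so; the remedy is the same.
- **The plan does not describe FETO-control contrasts by load.** Also correct: it says only that data will be analysed by load. If the sole question is whether experience goes with outcome, the treating centre is the relevant exposure. That is a reason to keep the treating-centre table as description. It does not protect a comparison of arms within those groups.
- **Diversion may not change the group.** Section 9.2 speaks of delivery, not of later treatment. No centre's load is given, and Section 4.0 already expects tertiary centres used to managing CDH. If the FETO centre is in the same load group as the intended one, the artefact is zero; if it is the lower-load centre, the direction reverses.
- **Rupture is not diversion.** The cited risks come from FETO in severe CDH, typically at 26-29 weeks, whereas placement here is at 30 to 31+6 weeks. Section 6.6.2 also provides for prolongation and balloon puncture after rupture. If half of an assumed 15% change group, the contrast falls from 5.9 to 3.0. This stands, and the table has no claim to being a bound.
- **The effect is small against sampling error.** True of most rows, but a systematic shift is not covered by the confidence interval, and it is cheap to avoid.

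Section 9.2 also accepts variation between postnatal centres as clinical reality. That acceptance concerns variation that may affect either group. It does not deal with a shift that arises in one arm only, and the passage on diverted deliveries is never linked to the case-load analysis.

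**Conclusion.** The point holds as a defect in one secondary analysis. The case-load grouping is left open, its natural reading is a variable that FETO can change, and the load itself is measured after randomisation. Comparisons of FETO with control within load groups can be biased when two conditions are met: diverted infants are treated at the FETO centre, and that centre is in a different load group from the intended one.

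A reader might infer that the plan moves FETO's worst cases out of low-load centres and so makes FETO look better there and worse in high-load centres. The documents do not support that. They give no centre loads, no diversion rate and no survival figure for diverted infants, so neither direction nor size can be derived. The 5.9 points, and the 1.0 with 5% diverted and 30% survival, only illustrate the stated assumptions.

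A reader might also infer that the main result is at risk. It is not: the intention-to-treat primary analysis does not use these groups, and the 98 per arm stands.

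**What to change.** Amend Section 9.2 as follows.

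- Define the load groups by the intended postnatal centre identified at eligibility, using that centre's annual load over a fixed period before enrolment in place of the load during the study.
- Keep every randomised case in its intended group, including fetal deaths and infants treated elsewhere.
- Make the groups complementary, for example under 6 v 6 or more per year, since exactly 6 now belongs to neither.
- Report the FETO-control difference in each group and the treatment-by-load interaction with 95% confidence intervals and no test, in line with the handling of secondary endpoints.
- Present results by actual treating centre as descriptive only.
- Align the label: one part of Section 9.2 plans this analysis in advance and another calls it post hoc.

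The cost is mainly wording. Section 5.2 requires the intended centre to be checked, but no section says that its identity is held in the database. Section 9.2 reports that two interim analyses have taken place, so the intended centre and its earlier load may have to be retrieved from eligibility records for cases already enrolled. The intended centre also measures the experience an infant actually received less exactly; the descriptive table covers that.

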#### Methods of analysis

We will analyze the primary and co-primary endpoints with the z-test for unpaired proportions (equal to the Pearson chi-square test) using a one-sided alpha of 2.5%. To control for multiplicity, we will use a hierarchical approach. If the trial is stopped for efficacy for the primary endpoint (survival at discharge) at one of the interim analyses based on the z-test, we will evaluate the co-primary endpoint (survival without oxygen dependency at 6 months) with the same test. As explained in the sample size section, the DSMC first decides whether more patients in the FETO arm have to be recruited in order to reach the required sample size. If it is not feasible to reach the required sample size, we will not perform the z-test for the co-primary endpoint.

For the primary and co-primary endpoints, we will compute the difference in proportions between the study arms as well as the relative risk, both with a standard two-sided 95% CI. These results are at least as important as the determination of statistical significance based on the z-test.

For the secondary endpoints, we will not perform statistical testing. For categorical endpoints, we will compute relative risks and differences in proportion with their respective 95% confidence intervals. For continuous endpoints, we will compute 95% confidence intervals on the difference in medians using the percentile bootstrap method. We will analyze time-to-event outcomes (days to discharge from neonatal intensive care unit, days until end of ventilatory support, days until release from ECMO support, days until full enteral feeding) with a 95% confidence interval for the median cumulative incidence of the event, with death used as a competing event 

Sources of error:

- The power of the study will be adversely affected by patient's non-compliance with the randomly assigned regimen.
- The number of centers recruiting for postnatal treatment cannot be anticipated at this time. This will by definition be uncontrollable, and it may influence the outcome in either group. This is an accepted source of error by the investigators because it is a clinical reality (this is an effectiveness or pragmatic trial). The organizers do not have funding, neither the power nor logistics for having all postnatal management at one location. Guidelines for standardization of postnatal treatment are therefore being issued (Appendix I), which will reduce the impact of this source of error. An important source of error may also be case load at each of these participating centers. For that reason a post hoc analysis will be made according to the case load during the study period.
- Subjects randomized to postnatal care who seek fetal intervention elsewhere, may reduce study power. The consortium of FETO centers will not perform FETO in patients eligible for the present study, outside the herein described RCT. This seems ethical as FETO-treatment for this particular severity group so far has not been offered by the FETO consortium, and to their knowledge neither elsewhere.
- The extent to which non-FETO centers will carry out FETO in patients that are eligible for the herein proposed RCT cannot be estimated. Maximum efforts will be done to reduce the number of such centers. One method is to include those centers based on the criteria outline below. During the course of this study, other prenatal treatment centers have expressed their interest to join this study. If they are not or less experienced, this may be a source of error. The steering committee has met on this issue and has defined empirically criteria for eligibility for study participation, following which they may apply locally for ethics committee approval and ultimately they may participate to the present study under the same conditions as herein.
- Preterm pre-labor rupture of the membranes and as a consequence preterm labor prior to in utero reversal of the occlusion, with as a consequence "incomplete" prenatal therapy as well as problems directly due to the inability or difficulties to remove the balloon, may result in lower than expected survival chances. When this happens, it will cause delivery at one of the FETO centers, therefore leading to a higher than expected number of babies delivered at these institutions. However this is inherent to the prenatal therapy and not avoidable. A separate secondary analysis may be done as to judge on the biological effect of the complete course of prenatal therapy (balloon insertion and balloon removal followed by birth in the un-occluded state), but again, results will be reported on an intention to treat - basis.
- In the fetal treatment arm there is the potential of patients not complying during the period the airways are plugged, presenting in an emergency at their local center, or for whatever reason not returning to the FETO center for balloon removal. This may adversely affect the outcome in the treatment group, lead to a higher than expected death rate in that arm. It could only be

discounted by post hoc exclusion. This will however not be done, as it is considered as an inherent risk of prenatal therapy. Such an effect may however be documented in a secondary analysis as described above.

- Prenatal medical imaging techniques may fail to recognize a concomitant congenital anomaly that is therefore only diagnosed after birth. Since serious associated anomalies are an independent predictor of outcome, and their numbers should be low, patients may not be equally distributed in both treatment arms. These patients will be excluded post hoc from analysis. It will include patients with serious genetic anomalies (not known at the time of FETO), undiagnosed structural cardiac or other structural anomalies that directly compromise neonatal outcome. Analysis of cases to be excluded will be overseen by the Data Monitoring and Safety Committee (also referred to as Oversight Committee).

- Adjustments for error sources: The aforementioned error sources will be dealt with, in part, by following all subjects eligible for the primary outcome regardless of whether the subject consents to randomization or refuses to comply with the assigned randomization. Since the magnitude of these effects cannot be known in advance, the Steering Committee will be charged with examining randomization refusal rates and refusal of randomized treatment. They may suggest to modify the sample size, the study design, or terminate the study for inadequate accrual/power/data quality/safety issues in consultation with the Oversight Committee, who has the final word about this.

- Missing data for the primary endpoints are very unlikely. In addition, the DSMC will review data entry and quality at every interim analysis such that we will detect eventual issues quickly such that we can act appropriately to ensure complete data. Inspection of data quality at the first two interim analyses confirms that missing values are very rare. If there is a missing value for the primary endpoint of survival at discharge, we will exclude the case from the study. If there is a missing value for the co-primary endpoint of survival without oxygen dependency at 6 months, we will not use the case for the analysis of the co-primary endpoint.

- If there is a missing value or for any secondary endpoint, we will exclude the case for the analysis of that specific endpoint. If we observe more than 10% missing values for a secondary endpoint, we will not analyze this endpoint. There is no need for statistical imputation of missing data.

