In fetuses with moderate CDH (=O/E LHR 25-34.9%, irrespective of the liver position as well as O/E LHR 35-44.9% with intrathoracic herniation of the liver) managed expectantly the estimated rate of postnatal survival is 60% or lower and the rate of broncho-pulmonary dysplasia in survivors is 33% or higher. It is not known whether percutaneous fetoscopic tracheal occlusion in this group would improve survival and reduce morbidity.

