## 9.0 STATISTICAL CONSIDERATIONS

### 9.1 Sample Size and Precision

Primary endpoint has been changed to survival at discharge. Initially, it was estimated that 55% of patients in control arm would be alive at discharge. Given that we have decided that an absolute increase in survival rate of 20% in FETO arm would be an improvement, clearly clinically relevant and realistic, we'd then assume a survival rate of 75% in FETO arm to determine sample size. An absolute increase of 15% would still be acceptable. Although it is of importance in this trial to

avoid continuation when there is evidence of effectiveness of FETO, it'd be undesired to underestimate the required sample size because of an overestimated survival rate in control arm. Therefore, we decided to use data from administrative review to estimate sample size. This resembles the internal pilot study method by Friede and Kieser. Using the overall average survival rate over the two groups (blinded data), which was 50.1%, we'd therefore use 40% vs 60% survival rate in control vs FETO arm. Based on blinded procedure, the size of the 'internal pilot', and the fact that an overall response rate of 50% maximizes required sample size there is no need to adjust type I and II error rates.

We use a group sequential design with overall one-sided alpha of 2.5% and a power of 80%. Formal interim analyses are scheduled for efficacy only, although the DMC retains the right to stop the trial for clear futility. We adopted the O'Brien-Fleming method to derive critical boundaries to stop the trial for efficacy. Five interim analyses are planned, after 40, 60, 70, 80, and 90% of sample size at final analysis. Using the abovementioned parameters and z-test for the difference in proportions, critical boundaries are obtained using PROC SEQDESIGN in SAS v9.3 (SAS Institute, Cary, USA).

Analysis	N per arm	Efficacy boundary	
		Difference in survival rates	p-value
Interim 1	40	0.365	0.0005
Interim 2	59	0.243	0.0036
Interim 3	69	0.209	0.0064
Interim 4	79	0.182	0.0099
Interim 5	89	0.162	0.0140
Final	98	0.146	0.0186

When deriving a sample size plan including formal boundaries to stop for futility, the overall sample size hardly changed. As a result, we left stopping for futility at the discretion of the Data Safety Monitoring Committee (DSMC).

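### Under the planned 40% control survival, the median cumulative incidence of NICU discharge will rarely be reached in controls, a two-sided interval is at best an even chance in either arm, and the plan gives no fallback

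*Combined protocol and SAP*

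**What the plan says.** The plan does no statistical testing on secondary endpoints; estimates and confidence intervals are their whole output. Section 9.2 (Methods of analysis) names four endpoints for a time-to-event analysis, namely "days to discharge from neonatal intensive care unit, days until end of ventilatory support, days until release from ECMO support, days until full enteral feeding", and summarises each "with a 95% confidence interval for the median cumulative incidence of the event, with death used as a competing event".

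Section 9.1 sets the survival at discharge used for design: "we'd therefore use 40% vs 60% survival rate in control vs FETO arm". That pair comes from the "overall average survival rate over the two groups (blinded data), which was 50.1" percent, with a 20-point difference placed around it. Before that, "it was estimated that 55% of patients in control arm would be alive at discharge". Section 2.0 says that under expectant management "the estimated rate of postnatal survival is 60% or lower".

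The documents do not define the median cumulative incidence. They name no interval method for it and do not say what is reported if it is not reached. They give no fixed-time estimate or between-arm contrast for these four endpoints, and no denominator (all randomized, live-born, or ECMO recipients only). The list of outcome measures in Section 9.2 assigns the day of death to NICU days when an infant dies, and this is not reconciled with treating death as a competing event.

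**The concern.** When death competes with the event, an infant who dies first never has the event. The cumulative incidence curve therefore does not climb to 1; it levels off at the share of infants who have the event before death. A median time exists only if that plateau is at least 0.50. Its upper confidence limit exists only if the lower confidence limit of the curve also gets to 0.50.

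NICU discharge is the clearest case. If deaths precede NICU discharge, the plateau is about the survival proportion, which the plan sets at 0.40 in controls.

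If the named summary turns out to be undefined, the analyst must choose a replacement after seeing the data. An obvious candidate, the median among survivors, conditions on survival, which FETO is expected to change.

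**Working it through.** **Inputs.** Section 9.1: survival 40% and 60%, 98 per arm, one-sided alpha 2.5%, power 80%, O'Brien-Fleming boundaries at 40, 60, 70, 80, 90 and 100% of the sample, pooled blinded survival 50.1%, earlier control value 55%. Assumed, because the documents do not say: the median is the time at which the curve reaches 0.50, all infants in an arm are in the denominator, and follow-up is complete.

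**Design reproduced.** The variance term is 0.4×0.6 + 0.6×0.4 = 0.48. The fixed design needs 0.48×(1.960+0.842)²/0.20² = 94.2 per arm. The O'Brien-Fleming constant for the stated looks is 2.083, and 80% power then needs 97.8, so 98 per arm. The final boundary is 2.083×√(0.48/97.8) = 0.146 with p = 0.0186. Both match Section 9.1, so 40% and 60% are the values on which the design rests.

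**Is the median reached?** With 98 infants the curve gets to 0.50 if at least 49 have the event: P(Bin(98, plateau) ≥ 49).

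**Is the upper limit finite?** The lower 95% limit of the plateau must be at least 0.50.
- Wald: 59/98 gives 0.505 and 58/98 gives 0.494, so 59 events are needed.
- Clopper-Pearson: 59/98 gives 0.498 and 60/98 gives 0.508, so 60 are needed.

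| Plateau | Source | Median reached | Upper limit finite, Wald | Clopper-Pearson |
|---|---|---|---|---|
| 0.40 | planned control | 0.03 | 0.00 | 0.00 |
| 0.45 | intermediate | 0.19 | 0.00 | 0.00 |
| 0.501 | pooled blinded rate | 0.55 | 0.03 | 0.02 |
| 0.55 | earlier control value | 0.86 | 0.18 | 0.13 |
| 0.60 | planned FETO | 0.98 | 0.53 | 0.45 |

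At 40% and 60%, both medians are reached in 0.0285×0.982 = 0.028 of trials. If the trial stops early at a control plateau of 0.40, the control median is reached in 0.13, 0.06 and 0.05 of trials at 40, 59 and 69 per arm. A lower limit alone, which needs at least 40/98 events (Wald), exists in about 47% of trials at a plateau of 0.40.

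**Events that can precede death.** Let s be the share of dying controls who have the event first. The plateau is 0.40 + 0.60s, which reaches 0.50 when s = 0.10/0.60 = 16.7%. The documents give no value for s, so these are assumed values:

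| s | Plateau | Median reached | Upper limit finite (Wald) |
|---|---|---|---|
| 10% | 0.46 | 0.24 | 0.00 |
| 20% | 0.52 | 0.69 | 0.06 |
| 30% | 0.58 | 0.96 | 0.37 |

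**ECMO release.** Among all infants the plateau could be far below 0.40. Among ECMO recipients it depends on a mortality that the documents do not give. No figure can be assigned.

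**What a fixed-time estimate would give.** Once the curves are flat, the control estimate is about 0.40 ± 1.96×√(0.24/98) = 0.40 ± 0.097. The difference is about 0.20 ± 1.96×√(0.48/98) = 0.20 ± 0.137.

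**The case against.** The strongest reply is that 40% is a planning value and not an observed control rate. It was obtained by splitting a pooled figure, with the stated aim of not underestimating the sample size. If control survival equals the pooled 50.1%, the median is reached in 55% of trials, and at 55% in 86%. This stands: a reader might infer that the control median cannot exist and that the analysis must return nothing, and the documents do not support that. It does not rescue the interval that the plan promises, which has a finite upper limit in only 3% and 18% of trials at those same rates.

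A reader might also carry the 3% over to all four endpoints. That is not supported either. An infant may come off ventilation or reach full feeding and die later, and the ECMO denominator is open.

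A third tempting inference is that no between-arm comparison remains. A median not reached in one arm and estimated in the other is still informative, and a lower limit will sometimes exist.

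Finally, the secondary morbidity objective does not rest on these four endpoints. The outcome list also includes pulmonary hypertension, sepsis, intraventricular hemorrhage, retinopathy, reflux and others, and the categorical ones are analysed by relative risks and differences in proportions, which this issue does not touch.

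**Conclusion.** The point holds within limits. For NICU discharge, with 40% control survival, all control infants in the denominator and deaths preceding discharge, the control median is reached in about 3% of trials with 98 per arm, and a two-sided interval is practically never available. Over control plateaus from 0.40 to 0.55, the median is reached in 3% to 86% of trials and the upper limit is finite in 0% to 18% (Wald). The FETO arm at its planned 60% nearly always has a point estimate but only about an even chance of a two-sided interval (53% Wald, 45% Clopper-Pearson).

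For end of ventilation and full feeding the same difficulty arises to a degree that the documents do not fix. For ECMO release it cannot be judged until the denominator is stated.

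These are untested secondary endpoints, so nothing here affects the primary, co-primary or other secondary analyses. The change is still worth making, because the stated summary mostly fails for NICU discharge under the plan's own assumptions and no substitute is named.

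**What to change.** For these four endpoints, make the main summary the cumulative incidence, with death as a competing event, at postnatal days fixed before any by-arm results for them are seen. Report the between-arm difference with a 95% CI. Days 28, 60 and 90 would serve as an illustration only; the documents give no basis for particular days.

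In the same text:
- define the denominator and time origin for each endpoint, including whether ECMO release is analysed in all infants, in centers offering ECMO, or in recipients only;
- reconcile the day-of-death rule for NICU days with the competing-event analysis;
- show the full curves for both arms;
- define the median and its interval method, and report it only if reached. Any median among survivors should be labelled descriptive.

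The cost is SAP wording and a few lines of code, with no new data. The one real downside is that the time points must be chosen in advance.
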